#### Amended Clinical Trial Protocol No. 05 SAR650984-ACT15319 - isatuximab

11-Jun-2019 Version number: 1

- a Time windows targeted for PK/pharmacodynamics and ADA sampling.
- Begin to the laboratory manual for sample collection, processing and shipping. REGN2810 PK samples to be collected: Cycle 1 predose (corresponding to SOI) and actual end of infusion (ie, EOI), EOI+ 4h, 168h, 336h, and 504h (predose second administration [Day 1 of Cycle 2]) after start of first dose; EOI of second administration (Day 22 [Day 1 of Cycle 2]); then Cycles 3 and 4: predose and EOI; subsequent cycles: predose and at 90 days after the last study treatment administration; isatuximab PK samples to be collected: Cycle 1 predose and EOI, EOI+ 1hand 168h (predose second administration, Day 8 of Cycle 1) after start of first dose; Cycle 1 Day 15 and Cycle 1 Day 22 (corresponding to Cycle 2 Day 1): predose and EOI; then Cycle 3 Day 1 predose; Cycle 4 Day 1: predose and EOI; subsequent cycles: Day 1 predose.
- c Predose sample: isatuximab PK or ADA assessment could be drawn at the same time just before REGN2810 administration.
- d Sample collected just before (within 5 minutes) the actual end of infusion of REGN2810.
- e Sample collected for REGN2810 could be drawn at the same time as the end of infusion sample of isatuximab.
- f REGN2810 sample collected strictly before the start of REGN2810 infusion.
- g S05 sample must be collected even if the second infusion of REGN2810 is not done or delayed.
- h Isatuximab PK and ADA samples to be collected each cycle until the last study treatment for PK and until follow-up for ADA or at the cut-off date, whichever comes first. However, collection can be stopped earlier or reduced upon notification from the Sponsor based on the updated knowledge of isatuximab immunogenicity and PK.
- i Sample collected just before actual end of infusion of isatuximab.
- *j* Predose sample for isatuximab collected strictly before the start of isatuximab infusion.
- k P03 sample must be collected even if the patient withdraws the study without receiving the second administration of isatuximab.
- I After start of study treatment, if 1 drug is prematurely discontinued, ADA samples for this drug will be collected on Day 1 of the 2 next cycles. If ADA test at the second cycle is positive or inconclusive, ADA testing will be repeated every 3 months until negative. The ADA sample collection for other drug should be done as planned.
- m During treatment phase, the ADA samples for REGN2810 must be collected before REGN2810 treatment administration at each time point: Cycle 1 Day 1, Cycle 1 Day 22 (predose Cycle 2), and on Day 1 every 3 cycles afterwards (ie, Cycle 5, Cycle 8, Cycle 11, Cycle 14 etc). In response to AEs of special interest, such as anaphylaxis or hypersensitivity, ADA samples closer to the event may be collected, based on the judgment of the Investigator and/or medical monitor.
- n During posttreatment follow-up period REGN2810 ADA samples are collected at 90 ±7 days after last study treatment and every 3 months thereafter until sample is negative (ASF01, ASF02...).
- o During treatment phase, the ADA samples for isatuximab must be collected before isatuximab treatment administration on Day 1 of each Cycle (could be drawn at the same time just before REGN2810 administration). ADA samples are not collected at Cycle 1 Day 8 or Cycle 1 Day 15.
- p During posttreatment follow-up period isatuximab ADA samples are collected at 90 ±7 days after last study treatment and every 3 months thereafter until sample is negative (APF01, APF02...).

Abbreviations: AB=antibody; ADA=anti-drug antibody; AP=antibody plasma (for REGN2810); AS=antibody serum (for isatuximab); EOI=end of IV infusion; P=plasma; PD=pharmacodynamic; PK=pharmacokinetic; RNT=relative nominal time; S=serum; SOI=start of IV infusion.

# 1.5.3 For Cohort C and Cohort D (tests for REGN2810 are not applicable for Cohort C if isatuximab monotherapy is administered)

Study phase									Treatr	ment pha	se								Post treatment
Cycle					Cyc	le 1					Су	cle 3		Cycle	4		Subseque	nt cycles	Follow-up period
Day within cycle		D	1		D4	D8	D15	D22 (	Cycle 2 Day	1)		) 1		D1			D 	1	90 ±7 days after last study treatment
Sample RNT (h) Ref: REGN2810 SOI	SOI	EOI	EOI+4h	-	72h	168h	336h	504h (SOI)	EOI	-	SOI	EOI	SOI	EOI	-	-	SOI	-	-
Sample Time window a	[-24h, SOI]	[-5 min,EOI]	±30 min	-	±5h	±24h	±48h	[-24h, SOI]	[-5 min, EOI]	-	[-24h, SOI]	[-5 min,EOI]	[-24h, SOI]	[-5 min,EOI]	-	-	[-24h, SOI]	-	-
Sample RNT (h) Ref: Isatuximab SOI	SOI	-	EOI	EOI+4h	72h	168h	336h	-	504h (SOI)	EOI	SOI	-	SOI	-	EOI	EOI+1h	SOI	-	-
Sample Time window a	-	-	±10 min	±30 min	±5h	±24h	±48h	-	-	±10 min	-	-	-	-	±10 min	±10 min	-	-	-
IMP administration (IV	/ infusion)																		
REGN2810	X	X						X	-X		X	X	X	X			Х		
Isatuximab		X	X						X	X		Х		X	-X			Х	
Pharmacokinetics b																			
REGN2810 Sample ID	S00 f	S01 d	S02 e	-	S03	S04	S05	S06 f,g	S07 d	-	S00 f	S01 d	S00 f	S01 d	-	-	S00 f	-	SF00
Isatuximab h Sample ID	P00 c	-	P01 i	P02	P03	P04	P05	P06 C, j,k	-	P07 i	P00 c,j	-	P00 c,j	-	P01 i	P02	P00 c,j	-	-
Immunogenicity (ADA	) /																		
REGN2810 m	AS00 f,m			-				AS01 f,m	-			-		-			AS00 f m	-	ASF00 n
Isatuximab h,o	AP00 C,O			-				AP01 C,O	-	-	AP00 C,O	-	AP00 C,O	-		-	AP00 c,h,o	-	APF00 h,p

#### Amended Clinical Trial Protocol No. 05 SAR650984-ACT15319 - isatuximab

11-Jun-2019 Version number: 1

- a Time windows targeted for PK/pharmacodynamics and ADA sampling.
- Edel Refer to laboratory manual for sample collection, processing and shipping. REGN2810 PK samples to be collected: Cycle 1 predose (corresponding to SOI) and actual end of infusion (ie, EOI), EOI+ 4h, 72h, 168h, 336h, and 504h (predose second administration [Day 1 of Cycle 2]) after start of first dose; EOI of second administration (Day 22 [Day 1 of Cycle 2]); then Cycles 3 and 4: predose and EOI; subsequent cycles: predose and at 90 days after the last study treatment administration); isatuximab PK samples to be collected: Cycle 1 predose and EOI, EOI+ 4h, 72h, 168h, 336h and 504h (predose second administration, Day 1 Cycle 2); Cycle 1 Day 22 (corresponding to Day 1 of Cycle 2): EOI; then Cycle 3 Day 1: predose, EOI, EOI+ 1h; subsequent cycles Day 1 predose.
- c Predose sample: isatuximab PK or ADA assessment could be drawn at the same time just before REGN2810 administration.
- d Sample collected just before (within 5 minutes) the actual end of infusion of REGN2810.
- e Sample collected for REGN2810 could be drawn at the same time as the end of infusion sample of isatuximab.
- f REGN2810 sample collected strictly before the start of REGN2810 infusion.
- g S06 sample must be collected even if the second infusion of REGN2810 is not done or delayed.
- h Isatuximab PK and ADA samples to be collected each cycle until the last study treatment for PK and until follow-up for ADA or at the cut-off date, whichever comes first. However, collection can be stopped earlier or reduced upon notification from the Sponsor based on the updated knowledge of isatuximab immunogenicity and PK.
- i Sample collected just before actual end of infusion of isatuximab.
- *i* Predose sample for isatuximab collected strictly before the start of isatuximab infusion.
- k P06 sample must be collected even if the patient withdraws from the study without receiving the second administration of isatuximab.
- I After start of study treatment, if 1 drug is prematurely discontinued, ADA samples for this drug will be collected on Day 1 of the 2 next cycles. If ADA test at the second cycle is positive or inconclusive, ADA testing will be repeated every 3 months until negative. The ADA sample collection for other drug should be done as planned.
- m During treatment phase, the ADA samples for REGN2810 must be collected before REGN2810 treatment administration at each time points: Cycle 1 Day 1, Cycle 1 Day 22 (predose Cycle 2), and on Day 1 every 3 cycles afterwards (ie, Cycle 5, Cycle 8, Cycle 11, Cycle 14 etc). In response to AEs of special interest, such as anaphylaxis or hypersensitivity, ADA samples closer to the event may be collected, based on the judgment of the Investigator and/or medical monitor.
- n During posttreatment follow-up period REGN2810 ADA samples are collected at 90 ±7 days after last study treatment and every 3 months thereafter until sample is negative (ASF01, ASF02...).
- o During treatment phase, the ADA samples for isatuximab must be collected before isatuximab treatment administration at each time (could be drawn at the same time just before REGN2810 administration). ADA samples are not collected at Cycle 1 Day 8 or Cycle 1 Day 15.
- p During posttreatment follow-up period isatuximab ADA samples are collected at 90 ±7 days after last study treatment and every 3 months thereafter until sample is negative (APF01, APF02...).

  Abbreviations: AB=antibody: ADA=anti-drug antibody: AP=antibody: AP=anti

S=serum; SOI=start of IV infusion.

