- Refer to the laboratory manual for sample collection, processing and shipping. REGN2810 PK samples to be collected: Cycle 1 predose (corresponding to SOI) and actual end of infusion (ie, EOI), EOI+ 4h, 72h, 168h, 336h, and 504h (predose second administration) after start of first dose; EOI of second administration (Day 22 [Day 1 of Cycle 2]); then Cycles 3 and 4: predose and EOI; subsequent cycles: predose and at 90 days after last study treatment administration; isatuximab PK samples to be collected: Cycle 1 predose and EOI, EOI+ 4h, 72h and 168h (predose second administration, Day 8 of Cycle 1) after start of first dose; Cycle 1 Day 15 and Cycle 1 Day 22 (corresponding to Cycle 2 Day 1): predose and EOI; then Cycle 3 Day 1 predose; Cycle 4 Day 1 predose, EOI, EOI+ 1h; subsequent cycles Day 1 predose. For the patients with NSCLC who are enrolled for Phase 2 Stage 1 after implementation of Amendment #5 at individual sites, no PK samples for REGN2810 and isatuximab will be collected.
- c Predose sample: isatuximab PK or ADA assessment could be drawn at the same time just before REGN2810 administration.
- d Sample collected just before (within 5 minutes) the actual end of infusion of REGN2810.
- e Sample collected for REGN2810 could be drawn at the same time as the end of infusion sample of isatuximab.
- f REGN2810 sample collected strictly before the start of REGN2810 infusion.
- g S06 sample must be collected even if the second infusion of REGN2810 is not done or delayed
- h Isatuximab PK and ADA samples to be collected each cycle until the last study treatment for PK and until follow-up for ADA or at the cut-off date, whichever comes first. However, collection can be stopped earlier or reduced upon notification from the Sponsor based on the updated knowledge of isatuximab immunogenicity and PK.
- i Sample collected just before actual end of infusion of isatuximab.
- j Predose sample for isatuximab collected strictly before the start of isatuximab infusion.
- k P04 sample must be collected even if the patient withdraws the study without receiving the second administration of isatuximab.
- 1 After start of study treatment, if 1 drug is prematurely discontinued, ADA samples for this drug will be collected on Day 1 of the 2 next cycles. If ADA test at the second cycle is positive or inconclusive, ADA testing will be repeated every 3 months until negative. The ADA sample collection for other drug should be done as planned.

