#### 12.3 TREATMENT PERIOD

#### 12.3.1 Cycle 1 (Day 1, Day 8 and Day 15)

The treatment window is  $\pm 1$  day for each of the QW administrations and  $\pm 2$  days for each of the Q3W administrations. The following procedures are to be performed/assessed on Day 1, Day 8 and Day 15 prior to study treatment administration unless specified otherwise:

- Physical examination: includes examination of major body systems (neurological, digestive, respiratory [signs and symptoms, respiratory rate] and lymph node examination).
- Body weight prior to starting infusion.

- Vital signs including blood pressure, heart rate, temperature, and respiration rate, prior to starting infusion of IMP, every hour during infusion, and at the end of infusion, and if clinically indicated during the infusion.
- Performance status (ECOG).
- All AEs/SAEs throughout the cycle, including AEs of new onset as well as worsening of baseline signs and symptoms.
- Concomitant medications from registration and used throughout the cycle.
- Study treatment administration: REGN2810 on Cycle 1 Day 1 (only in cohorts receiving isatuximab and REGN2810 combination); isatuximab on Cycle 1 Day 1, Cycle 1 Day 8 and Cycle 1 Day 15 (isatuximab is not administered on Cycle 1 Day 8 and Cycle 1 Day 15 in Cohort C and Cohort D).

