2.1.5 Pharmacokinetic variables

The PK sampling times for isatuximab and REGN2810 were provided in the PK/PD flowchart in Section 1.5 of the protocol.

The following PK parameters (listed in [Table 3](#)) will be calculated with PKDMS software (Pharsight) V3.0, using non-compartmental method from isatuximab and REGN2810 concentrations after the first administration on Cycle 1. The parameters will include, but may not be limited to the following:

Table 3 - List of pharmacokinetic parameters and definitions

Parameters	Analyte		Definition
	REGN2810	Isatuximab	
C _{eo1}	X	X	Concentration observed at the end of intravenous (IV) infusion
C _{max}	X	X	Maximum concentration observed
t _{max}	X	X	Time to reach C _{max}
C _{last}	X	X	Last concentration observed above the lower limit of quantification
t _{last}	X	X	Time of C _{last}
AUC _{0-21d}	X		Area under the concentration versus time curve calculated using the trapezoidal method over the dosing interval (21 days)
AUC _{0-7d} or AUC _{0-21d}		X	Area under the plasma concentration versus time curve calculated using the trapezoidal method over the dosing interval (7 days, and for cohorts C and D: 21 days)

C_{trough} are defined as sample collected just before treatment administration during repeated dosing.

In addition, populations PK approaches may be used for both compounds and PK estimates may be used to conduct exploratory exposure-response analyses for safety and efficacy and PK/PD analyses for relevant biomarkers. If done, the data generated will be reported in stand-alone report(s).

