2.4.7.1.2 Overall treatment: C_{trough} and C_{eoI}

C_{trough} defined as a sample collected before dosing, and in a time window of 12 to 16 days after the previous infusion for the Q2W administration, or in a time window of 6 to 8 days after the previous infusion for the QW administration will be included in the descriptive analysis irrespectively of interruption of infusion. However C_{trough} drawn outside collection of time window described in the protocol PKPD flowchart or collected after dose deviation higher than $\pm 50\%$ from intended dose will be excluded from the analyses.

C_{eo} collected after significant infusion interruption, drawn outside collection of time window described in the protocol PKPD flowchart or collected after dose deviation higher than $\pm 50\%$ from intended dose will be excluded from the analyses.

Individual C_{trough} and C_{eo} will be listed and summarized with same descriptive statistics as above by cohort and possibly overall.

Mean ($\pm SE$) of C_{trough} will be plotted over treatment phase by cohort and possibly overall for isatuximab and for REGN2810.

Individual C_{trough} ratio and C_{eo} ratio (described in [Table 5](#)) will be listed and summarized by descriptive statistics by cohort and possibly overall as described above.

Table 5 - C_{trough} and C_{eo} ratio

Analyte	C_{trough}	C_{eo}
Isatuximab	C2D1 vs C1D8	C2D1 vs C1D1
	C4D1 vs C1D8	C4D1 vs C1D1
REGN2810	C4D1 vs C1D22	C4D1 vs C1D1

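### SAP Table 5 gives no valid isatuximab trough ratio for Cohorts C and D, because its Cycle 1 Day 8 denominator is a mid-interval sample there

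*Protocol*

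**What the plan says.** Below, C1D8 means Cycle 1 Day 8, and so on.

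- **The ratios.** SAP Section 2.4.7.1.2, Table 5, sets the isatuximab Ctrough ratios as C2D1 vs C1D8 and C4D1 vs C1D8. For REGN2810 it uses C4D1 vs C1D22. The ratios "will be listed and summarized by descriptive statistics by cohort and possibly overall as described above". No cohort is excepted.
- **What a trough is.** SAP Section 2.1.5 says troughs "are defined as sample collected just before treatment administration during repeated dosing". Section 2.4.7.1.2 also requires a set time since the previous infusion: 12 to 16 days for Q2W dosing, or "in a time window of 6 to 8 days after the previous infusion for the QW administration". It gives no such window for Q3W.
- **Dosing in Cohorts C and D.** Protocol Section 12.3.1 states that "isatuximab is not administered on Cycle 1 Day 8 and Cycle 1 Day 15 in Cohort C and Cohort D". The administration table in Section 1.2 agrees.
- **Sampling in Cohorts C and D.** Footnote b to Protocol Section 1.5.3 lists "Cycle 1 predose and EOI, EOI+ 4h, 72h, 168h, 336h and 504h (predose second administration, Day 1 Cycle 2". The first predose sample after the first dose is therefore at 504 h, and the 168 h sample precedes no dose.
- **Sampling in the weekly-loading cohorts.** The corresponding footnote in Section 1.5.1 reads "72h and 168h (predose second administration, Day 8 of Cycle 1) after start of first dose". There, Day 8 is a genuine predose sample.
- **An adaptation made elsewhere.** For the isatuximab AUC, SAP Table 3 distinguishes the schedules: "7 days, and for cohorts C and D: 21 days". Table 5 makes no such distinction.

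**The concern.** Table 5 uses one denominator for two dosing schedules, and that denominator is a trough under only one of them. The SAP adapts the AUC interval to Cohorts C and D and gives Q3W REGN2810 a trough-over-trough ratio, so this looks like an oversight.

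It can go wrong in two ways. A programmer working from visit labels would compute C1D8-based ratios in Cohorts C and D. A simple elapsed-time check would not stop this: the 168 h sample has a ±24 h collection window in Section 1.5.3, which is exactly 6 to 8 days. A programmer applying the trough definition strictly would have no C1D8 trough and could compute neither ratio.

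At stake is the interpretation of a secondary PK summary. Protocol Section 4.3.2 explains that Q3W dosing is to be tested because the loading period may not be needed. A reader comparing schedules would look at isatuximab exposure over time, and an overall summary could mix ratios that measure different things under one label.

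**Working it through.** The documents give no numerical ratio to reproduce, so this is a sketch of what Table 5 would return.

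**Inputs.** Half-lives of 18 days and, re-estimated, 28 days (Protocol Section 4.3.2). Cycle length 21 days. Isatuximab doses at days 0, 21 and 42 in Cohorts C/D, and at days 0, 7, 14, 21 and 42 in the weekly-loading cohorts. Sampling just before any dose at day 7 (C1D8), day 21 (C2D1 = C1D22) and day 63 (C4D1).

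**Assumptions (mine).** One compartment, linear elimination, equal doses, infusion treated as a bolus. With half-life h, one unit dose leaves k(t) = 2^(−t/h) after t days, and doses add.

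**Cohorts C and D.**
- C1D8 = k(7)
- C2D1 = k(21)
- C4D1 = k(21) + k(42) + k(63)

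| Quantity | h = 18 d | h = 28 d |
|---|---|---|
| C1D8 | 0.764 | 0.841 |
| C2D1 | 0.445 | 0.595 |
| C4D1 | 0.445 + 0.198 + 0.088 = 0.732 | 0.595 + 0.354 + 0.210 = 1.158 |
| Table 5: C2D1/C1D8 | 0.58 | 0.71 |
| Table 5: C4D1/C1D8 | 0.96 | 1.38 |
| Trough over trough: C4D1/C2D1 | 1.64 | 1.95 |

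C2D1/C1D8 = k(21)/k(7) = 2^(−14/h). Both samples follow the same single dose, so this ratio is decay only.

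C4D1/C1D8 = (C4D1/C2D1) × 2^(−14/h). It is the trough accumulation multiplied by 14 days of decay. The understatement is 1 − 2^(−14/h): 1 − 0.583 = 42% at 18 days and 1 − 0.707 = 29% at 28 days. The ratio falls below 1 only for half-lives under about 18.8 days.

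**Sensitivity.** For assumed half-lives of 10 to 35 days, C4D1/C1D8 runs from 0.49 to 1.59, C4D1/C2D1 from 1.29 to 2.10, and the understatement from 62% to 24%.

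**Weekly-loading cohorts, for contrast.**
- C2D1/C1D8 = 1 + k(7) + k(14) = 2.35 (18 d) or 2.55 (28 d). Both samples are 7-day troughs, because C2D1 falls 7 days after the Day 15 dose. This ratio is like for like.
- C4D1/C1D8 = [k(21) + k(42) + k(49) + k(56) + k(63)]/k(7) = 1.31 (18 d) or 2.03 (28 d). Both samples are true troughs, but the numerator is taken 21 days after a dose and the denominator 7 days after.

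**Trough windows.** In Cohorts C/D, C2D1 and C4D1 are taken 21 days after the previous infusion and fit neither the 6–8 day nor the 12–16 day window. The same is true of isatuximab predose samples from Cycle 3 in the weekly-loading cohorts, and of REGN2810 troughs throughout.

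**The case against.** A reader might infer that Table 5 hides isatuximab accumulation in Cohorts C and D. The documents do not support that.

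- **Other outputs show it.** Table 5 also has end-of-infusion ratios, which compare like with like in Cohorts C/D. In the same sketch, C2D1/C1D1 = 1 + k(21) = 1.45 (18 d) or 1.60 (28 d), and C4D1/C1D1 = 1 + k(21) + k(42) + k(63) = 1.73 or 2.16. SAP Section 2.4.7.1.2 also lists and summarises individual troughs and plots mean troughs over the treatment phase by cohort. One caveat remains: the Section 1.5.3 flowchart puts the later end-of-infusion sample at Cycle 4, while its footnote b puts it at Cycle 3. These need reconciling before the C4D1 end-of-infusion ratio can be relied on.
- **The worst case uses the older half-life.** At 28 days, C4D1/C1D8 is 1.38. Accumulation is understated but still visible.
- **The numbers are model-based.** Protocol Section 4.3.2 describes non-linear, target-mediated kinetics in myeloma. Less of this is hypothesised in prostate cancer, but that is untested.
- **No rule uses the ratio.** The SAP does not call it an accumulation ratio. Opening Cohorts C and D depends on the efficacy signal and the totality of data, and their primary objective is response rate. Both cohorts are optional, and pooling is only a possibility.
- **The strict reading gives a blank, not a bias.** Under the SAP's own definition the Day 8 sample in Cohorts C/D is not a trough, so the understatement arises only if the visit label is followed.

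All of this stands and limits the consequence. None of it makes C1D8 a usable trough denominator in Cohorts C and D, and the strict reading still leaves those cohorts without a prespecified isatuximab trough ratio.

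**Conclusion.** The point holds as a specification defect in SAP Table 5: as written, Cohorts C and D have no valid isatuximab trough ratio. By visit label, C2D1/C1D8 measures decay within one interval, and C4D1/C1D8 understates trough accumulation by about 29% at a 28-day half-life and 42% at 18 days. By strict definition, neither can be computed.

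The dosing and sampling facts come directly from the documents. The percentages rest on one-compartment linear kinetics and the protocol's two half-lives. The consequence is modest: a descriptive secondary PK summary in conditional cohorts, with no effect on response rate or any decision rule. The correction is worth making because the table is wrong for these cohorts and cheap to repair.

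**What to change.** In SAP Section 2.4.7.1.2:

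1. Add an isatuximab row to Table 5 for Cohorts C and D: Ctrough C4D1 vs C2D1 (that is, C1D22), matching the REGN2810 row.
2. Restrict the C1D8-based isatuximab ratios to the weekly-loading cohorts, with a note that C4D1/C1D8 there sets a 21-day trough against a 7-day trough.
3. State that the two kinds of ratio are not pooled in any overall summary.
4. Add a Q3W trough window. The present windows cover QW and Q2W, and Q2W is not a schedule in this trial. Without a Q3W window the new row would itself have no qualifying samples.

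The cost is one table row and a few lines of SAP text. The C2D1 and C4D1 predose samples for Cohorts C and D are already scheduled in both the flowchart and footnote b of Protocol Section 1.5.3, so no sampling changes. Separately, reconcile that flowchart and footnote on whether the later end-of-infusion sample belongs to Cycle 3 or Cycle 4.

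### Protocol 1.5.3 (Cohorts C and D): footnote b places the isatuximab end-of-infusion samples at Cycle 3, the table places them at Cycle 4, and one descriptive SAP ratio depends on the Cycle 4 sample

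*Protocol*

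**What the plan says.** Footnote b to the PK flowchart for Cohorts C and D (protocol 1.5.3) lists the samples to be taken. For isatuximab after Cycle 2 it says "then Cycle 3 Day 1: predose, EOI, EOI+ 1h; subsequent cycles Day 1 predose". Cycle 4 is not named, so it falls under subsequent cycles and gets a predose sample only.

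The isatuximab sampling-time row of the table in the same section runs, from Day 22 to the end of Cycle 4, "504h (SOI) EOI SOI - SOI - EOI EOI+1h". Set against the column headings, this is a start-of-infusion (predose) sample alone at Cycle 3, then start of infusion, EOI and EOI+1h at Cycle 4.

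The corresponding footnotes for the other cohorts place the EOI sample at Cycle 4:
- 1.5.1: "then Cycle 3 Day 1 predose; Cycle 4 Day 1 predose, EOI, EOI+ 1h; subsequent cycles Day 1 predose"
- 1.5.2: "then Cycle 3 Day 1 predose; Cycle 4 Day 1: predose and EOI; subsequent cycles: Day 1 predose"

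SAP Section 2.4.7.1.2, Table 5, lists the isatuximab trough and EOI ratios for Cycle 4 as "C4D1 vs C1D8 C4D1 vs C1D1". It has no EOI ratio for Cycle 3. The ratios "will be listed and summarized by descriptive statistics by cohort and possibly overall as described above", with no exception for Cohorts C and D.

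**The concern.** The table and the footnote are both operative instructions to sites, and both cannot be followed as written. A missed end-of-infusion sample cannot be recovered later. A site that works from the footnote would draw EOI and EOI+1h at Cycle 3 and nothing after the infusion at Cycle 4. The SAP would then ask for a C4D1/C1D1 EOI ratio whose numerator had not been collected. Sites reading the section differently would also leave the ratio available for some patients in a cohort and not for others, for reasons unrelated to the patients.

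**Working it through.** There is no plan figure to reproduce. The check is an alignment of the table with its footnote, followed by a count of samples.

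**1. Is the conflict an artefact of the extracted table?** The 1.5.3 table has 4 (Cycle 1 Day 1) + 3 (Days 4, 8, 15) + 3 (Day 22) + 2 (Cycle 3) + 4 (Cycle 4) + 2 (subsequent cycles) + 1 (follow-up) = 19 columns. The isatuximab sampling-time row and the isatuximab sample-ID row each have 19 entries. Columns 11–12 are Cycle 3 and columns 13–16 are Cycle 4.
- Time row: columns 11–12 give SOI and blank; columns 13–16 give SOI, blank, EOI, EOI+1h.
- Sample-ID row: columns 11–12 give P00 and blank; columns 13–16 give P00, blank, P01, P02.
- Window row: the two ±10 min windows after Day 22 stand in columns 15 and 16, under Cycle 4.

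Three rows agree, so the Cycle 4 placement is not a misread table.

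**2. Is the whole footnote out of step?** No. Its REGN2810 text, "then Cycles 3 and 4: predose and EOI", matches the table. Only the isatuximab text differs.

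**3. Isatuximab samples per patient under each version**

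| | Cycle 3 Day 1 | Cycle 4 Day 1 | Total |
|---|---|---|---|
| 1.5.3 table | 1 (predose) | 3 (predose, EOI, EOI+1h) | 1 + 3 = 4 |
| 1.5.3 footnote b | 3 (predose, EOI, EOI+1h) | 1 (predose) | 3 + 1 = 4 |

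**4. Effect on the isatuximab EOI ratios in SAP Table 5**

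| Ratio | Under the table | Under footnote b |
|---|---|---|
| C2D1 / C1D1 | both terms collected | both terms collected |
| C4D1 / C1D1 | both terms collected | numerator not collected |

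The Day 22 (Cycle 2 Day 1) EOI sample is P07 in the table and is also listed in footnote b, so the C2D1/C1D1 ratio survives either way. So does the Cycle 4 predose sample.

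**5. Ceiling on patients.** Protocol 13.1 gives 49 patients for an mCRPC cohort and 36 for an NSCLC cohort on the alternative schedule, so at most 49 + 36 = 85. Only those who reach Cycle 4 Day 1 could contribute. Without delays that visit is Day 3 × 21 + 1 = 64, and the first scheduled tumour assessment is at 63 ± 7 days, so some patients may have stopped by then.

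**The case against.** The strongest reply is that little is at stake and sites will probably follow the table. It carries sample IDs and windows at Cycle 4 and none for isatuximab EOI at Cycle 3. Protocol 9.2.1 points to the flowchart for sampling times, and sites also work from a laboratory manual that is not among the documents. Most of this stands as mitigation. It does not settle the conflict, because footnote b is part of that same flowchart section and is the text that lists the samples to collect.

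Four stronger readings are tempting, and the documents do not support them.
- *PK is a main question of these cohorts.* Protocol 6.3 gives Cohorts C and D the same objectives as the other cohorts of the same tumour type, so response rate is primary and PK secondary. The stated reasons for the schedule are practicality and that loading may not be needed for activity. No PK comparison between schedules is specified.
- *Accumulation cannot be assessed at all.* Only one of the two isatuximab EOI ratios is exposed.
- *The Cycle 3 samples would be wasted.* The SAP lists and summarises individual EOI concentrations apart from the ratios, and allows population PK. Its exclusion of values "drawn outside collection of time window described in the protocol PKPD flowchart" concerns sampling windows and does not expressly bar a Cycle 3 visit. Those samples still could not supply the C4D1 numerator.
- *All 85 patients would lose the value.* That needs both optional cohorts to open and fill, every patient to reach Cycle 4, and every site to prefer the footnote.

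It can also be said that Table 5 fits these cohorts poorly in any case. Its isatuximab trough ratios use C1D8 as denominator, yet Cohorts C and D receive no isatuximab on Day 8, and the trough windows in that SAP section cover QW and Q2W but not Q3W. This is correct, and correcting footnote b will not cure it. It does not lessen the present point, since the EOI ratio at C4D1 is well defined for a Q3W schedule.

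**Conclusion.** The contradiction is real and footnote b is wrong as written. It stands alone against the 1.5.3 table, the table and footnote of 1.5.1, the Cycle 4 EOI placement in 1.5.2, and SAP Table 5. Comparison with the 1.5.1 footnote suggests that the words separating Cycle 3 from Cycle 4 were dropped; that is an inference, and nothing in the documents indicates a deliberate change of schedule.

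The consequence is small and conditional. It arises only if Cohort C or D opens and a site follows the footnote. It then removes the numerator of the isatuximab C4D1/C1D1 EOI ratio for that site's patients, within a ceiling of 49 in Cohort C and 36 in Cohort D, reduced to those who reach Cycle 4. The ratio is descriptive. No efficacy analysis, safety analysis or stage decision rule uses it. This is an inconsistency worth correcting, not a flaw in the design.

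**What to change.** Before either cohort opens, amend the isatuximab part of footnote b in protocol 1.5.3 to read, from Cycle 3 on: Cycle 3 Day 1, predose; Cycle 4 Day 1, predose, EOI and EOI+1h; subsequent cycles, Day 1 predose. That brings it into line with the 1.5.3 table and SAP Table 5. Check that the laboratory manual carries the same schedule. If the sponsor in fact intended Cycle 3, the table and the SAP ratio for these cohorts would have to change instead.

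The cost is one footnote edit. Each patient still gives four isatuximab samples across Cycles 3 and 4, so there is no added burden, and the EOI ratios in SAP Table 5 need no change.
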